## 16.24 Analysis Plans

All the relevant results pertaining to toxicity, MTD, response, timed endpoints and laboratory correlates will be examined in an exploratory and hypothesis-generating fashion. The small sample size and the heterogeneous patient population associated with phase I studies restricts the generalizability of the results. Any notable statistical result should only be viewed as preliminary evidence for the Phase II component rather than a definitive finding in and of itself.

#### 16.241 Adverse Events / Toxicity Profile (Goal 2.1.11)

The primary endpoint of the phase I portion is the incidence of dose-limiting toxicity. A dose-limiting toxicity is defined in section 7.61. Toxicities will be assessed using the CTEP Active Version of the CTCAE. Non-hematologic toxicities will be evaluated via the ordinal CTC standard toxicity grading. Hematologic toxicity measures of thrombocytopenia, neutropenia, and leukopenia will be assessed using continuous variables as the outcome measures (primarily nadir) as well as categorization via CTC standard toxicity grading.

These data will be assessed in evaluating the tolerability of the regimen for future studies. All patients meeting the eligibility criteria who have signed a consent form and have begun treatment will be considered evaluable for dose-limiting toxicity. Incidence of DLT will be estimated by the number of patients with DLT divided by the total number of evaluable patients. No more than three patients will receive the first cycle of combination immunotherapy (Pembrolizumab and cryoablation and DC injections, i.e. Cycle 2 of the overall treatment plan) at any time during Phase I of the study.

For a comprehensive picture of toxicity profile, we will also summarize the incidence of other significant toxicities as defined in Section 8 or as a Grade 3 or higher adverse event otherwise not described in Section 8, that is possibly, probably, or definitely related to treatment. The number and severity of all adverse events (overall and by dose level) will be tabulated and summarized in this patient population. The Grade 3+ adverse events will also be described and summarized in a similar fashion. This will provide an indication of the level of tolerance for this treatment combination in this patient group. Frequency distributions, graphical techniques and other descriptive measures will form the basis of these analyses. Further longitudinal analysis techniques will be employed to explore the adverse event profile over time.

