#### 1.44 Safety considerations from DC therapy

DC vaccine therapy clinical trials in B-cell NHL have thus far demonstrated no significant adverse events or autoimmunity (Table 1). DC immunotherapy has been used for many different tumors types where adverse events (such as induced autoimmunity) were monitored. Importantly, very few significant adverse effects of DC vaccination have been reported and DC immunotherapy clinical trials performed to date have shown no evidence of resultant generation of autoimmunity. To date, 86 patients have been treated with DC therapy without any serious drug related toxicity reported. In our trial LS1081, 15 patients were treated without any autoimmunity or grade 3 or higher adverse events attributable to treatments. The most common adverse event was injection site pain, more often with cryoablation, that usually resolved within 2 days of treatments (Table 2).

Table 1. Summary of clinical trials using dendritic cell vaccines for NHL

Histopath Diagnosis	Phase (N)	Ag source	DC source	Delivery	Safety	Clinical outcome
Follicular (Hsu, Benike et al. 1996)	I (4)	Idiotype	Blood *	IV	No Grade 3-4 AEs; no AI	1 CR, 1 PR, 1 molecular CR
Follicular (Timmerman, Czerwinski et al. 2002)	I (10) II (25)	Idiotype	Blood *	IV	No Grade 3-4 AEs; no AI	I: 3 CR, 1 PR, 6 PD II: 16 CR, 7 PR, 2 PD
Follicular, lymphoplasmacytoid (Di Nicola, Zappasodi et al. 2009)	I (18)	Heat-shocked autologous tumor cells	Matured from monocytes	SC	No Grade 3-4 AEs; no AI	3 CR, 3 PR, 8 SD, 4 PD
Follicular (Kolstad, 2015)	I (14)	in situ loading via intra-tumor injection	Immature DC from monocytes	Intra-tumor	No Grade 3-4 AEs; No AI	2 CR, 3 PR
Indolent B-cell NHL (LS1081 preliminary results)	I (Arm A: 10; Arm B: 5)	Arm A: in situ via intra-tumor injections Arm B: tumor lysate	Matured from monocytes	Arm A: intra-tumor Arm B: intradermal	No Grade 3-4 AEs; no AI	Arm A: 5 PR Arm B: 1 CR, 2 PR

Blood-derived DC used gradient centrifugation and adhesion method. DCs were characterized by negative phenotype markers without description of maturation markers normally used in release criteria. (AI = autoimmunity. CR = complete remission. IV = intravenous. PD = progressive disease. PR = partial remission. SC = subcutaneous. SD = stable disease.)

Table 2. Summary of adverse events attributable to treatments in LS1081 study

[figure not shown]
Adverse Event		Grade							
		1		2		3		4	
Type	Arm	N	%	N	%	N	%	N	%
Urticaria	A	2	25.0	1	12.5				
Bronchospasm	A			1	12.5				

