## 10.6 Required Routine Reporting

### 10.61 Baseline and Adverse Events Evaluations

Pretreatment symptoms/conditions to be graded at baseline and adverse events to be graded at each evaluation.

Grading is per CTCAE v4.0 **unless** alternate grading is indicated in the table below:

CTCAE System/Organ/Class (SOC)	Adverse event/Symptoms	Baseline	Each evaluation
Investigations	Platelet count decreased	X	X
	Neutrophil count decreased	X	X
Blood and lymphatic system disorders	Anemia	X	X
Gastrointestinal disorders	# of stools	X	
	Diarrhea		X
	Nausea	X	X
	Vomiting	X	X
Respiratory, thoracic and mediastinal disorders	Cough	X	X
	Dyspnea	X	X
	Pneumonitis	X	X
Skin and subcutaneous tissue disorders	Rash maculo-papular	X	X

10.62 Submit via appropriate MCCC Case Report Forms (i.e., paper or electronic, as applicable) the following AEs experienced by a patient and not specified in Section 10.6:

10.621 Grade 2 AEs deemed *possibly, probably, or definitely* related to the study treatment or procedure.

10.622 Grade 3 and 4 AEs regardless of attribution to the study treatment or procedure.

10.623 Grade 5 AEs (Deaths)

10.6231 Any death within 30 days of the patient's last study treatment or procedure regardless of attribution to the study treatment or procedure.

10.6232 Any death more than 30 days after the patient's last study treatment or procedure that is felt to be at least possibly treatment related must also be submitted as a Grade 5 AE, with a CTCAE type and attribution assigned.

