### 16.322 Secondary Outcome Analyses:

These analyses will include all patients meeting the eligibility criteria who have signed a consent form and have begun treatment. Analyses will include all patients enrolled in the Phase II portion of the study and analysis of each cohort separately.

16.323 Complete response (Goal 2.2.21): The response rate will be calculated, as above, in each individual cohort as supplementary to the primary analysis.

16.324 Progression free survival, treatment free survival, and duration of response (Goal 2.2.22):

Survival time is defined as the time from registration to death due to any cause. The distribution of survival time will be estimated using the method of Kaplan-Meier (Kaplan E 1958). In addition, the overall survival rate at 2 years after registration will be reported.

Treatment free survival time is defined for all evaluable patients who have achieved a response as the time from registration to next treatment or death due to any cause. The distribution of treatment-free survival will be estimated using the method of Kaplan-Meier. In addition, the disease-free survival rate at 2 years after registration will be reported.

Duration of response is defined for all evaluable patients who have achieved a PR or CR as the date at which the patient's objective status is first noted to be a response to the earliest date progression is documented. The distribution of duration of complete response will be estimated using the method of Kaplan-Meier.

16.325 Adverse Events (Goal 2.2.23): All eligible patients that have initiated treatment will be considered evaluable for assessing adverse event rate(s). The maximum grade for each type of adverse event at each evaluation will be recorded for each patient, and frequency tables will be reviewed to determine patterns. Additionally, the relationship of the adverse event(s) to the study treatment will be taken into consideration. Longitudinal analysis techniques will be utilized to determine the effect

of time on treatment adverse events.

16.326 Quality of Life (Goal 2.2.24):

Quality of life as measured using the FACT-Lym will be utilized. The assessment will be scored according to the scoring algorithm. Changes from baseline will be calculated at each assessment time points. Mean change scores at each time point will be calculated to determine if quality of life is reduced over the course of treatment. Longitudinal techniques will be employed to describe changes over time.

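### The adverse event tables promised in Sections 16.241 and 16.325 cannot be filled from what Section 10.6 collects, and low-grade injection toxicities fall in the gap

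*Combined protocol and SAP*

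**What the plan says.** **Analysis text.** For Phase I, Section 16.241 states: "The number and severity of all adverse events (overall and by dose level) will be tabulated and summarized in this patient population". It then says that Grade 3+ events will also be described, so the full tabulation must include Grades 1 and 2. For Phase II, Section 16.325 states: "The maximum grade for each type of adverse event at each evaluation will be recorded for each patient", and adds longitudinal analysis of events over time.

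**Collection text.** Section 10.61 sets a solicited list: "Pretreatment symptoms/conditions to be graded at baseline and adverse events to be graded at each evaluation". The terms graded at each evaluation are platelets, neutrophils, anemia, diarrhea, nausea, vomiting, cough, dyspnea, pneumonitis and maculo-papular rash. Section 10.62 then covers "the following AEs experienced by a patient and not specified in Section 10.6". Its lowest threshold is "10.621 Grade 2 AEs deemed *possibly, probably, or definitely* related to the study treatment or procedure". Above that level, events of Grade 3 or 4 are taken whatever their cause, and so are Grade 5 events (deaths within 30 days, or later if at least possibly related).

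**Expected toxicity.** Section 7.116 lists known potential toxicities of DC injection, among them injection-site reaction, generalized urticaria and other allergic reactions. On the predecessor trial LS1081, Section 1.44 reports: "The most common adverse event was injection site pain, more often with cryoablation". It gives no grade for that event.

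**The concern.** The analysis sections describe a complete record of events, and the collection section describes a partial one. For a term outside the Section 10.61 list, a blank can mean that the event did not occur or that it occurred below the submission threshold. The tables cannot tell these apart.

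The gap falls on the terms of most interest in this trial. Section 15.27 gives the known toxicities of the DC product as unknown, and Section 15.36 says there are no adult safety data for Prevnar13, so this trial is a natural source of both. Section 8.12 allows DC treatment to be delayed for dermatological events of Grade 2 or lower. A Grade 1 urticaria could thus alter a patient's schedule without being a required submission. Meanwhile nausea and cough are recorded at every grade. A reader of the final table would be comparing rows collected under different rules, with nothing in Section 16 to say so.

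The longitudinal summary in Section 16.325 has the same weakness. An unlisted, related event that falls from Grade 2 to Grade 1 between evaluations drops out of the required data and looks resolved.

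**Working it through.** **1. What is required, by type of term (Sections 10.61 and 10.62)**

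| Event | On the 10.61 list | Not on the list |
|---|---|---|
| Grade 1 | submitted | not required |
| Grade 2, unrelated | submitted | not required |
| Grade 2, related | submitted | submitted |
| Grade 3–4, any attribution | submitted | submitted |

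One route reopens the two empty cells. Section 10.1(f) sends expedited events into routine data as well. It is narrow: the Section 10.41 table asks for no expedited report of Grade 1 or 2 events without hospitalization of at least 24 hours.

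**2. The rules applied to Table 2 (LS1081, as extracted)**

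| Term | Entries | Required under 10.6? |
|---|---|---|
| Urticaria | Grade 1: 2; Grade 2: 1 | Grade 2 only |
| Bronchospasm | Grade 2: 1 | yes |
| Injection site reaction | Grade 2: 1 | yes |
| Lymph node pain | Grade 2: 1 | yes |
| Rash maculo-papular | Grade 2: 1 | yes (listed) |
| Vasovagal reaction | Grade 3: 1 | yes |

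Six of the eight entries are kept and two are lost. Both lost entries are urticaria; the other five terms lose nothing.

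**3. Size for urticaria**

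- Implied denominator: 2 / 0.25 = 8.
- If the three entries are three patients: any-grade rate (2 + 1)/8 = 37.5%; rate from required data 1/8 = 12.5%. Two thirds of the affected patients are lost.
- If the Grade 2 patient is also one of the Grade 1 patients: 2/8 = 25.0% falls to 1/8 = 12.5%, a loss of half.
- Table 1 gives this arm as 10 patients, not 8, and the documents do not reconcile the two. On 10 patients the first case is 3/10 = 30% falling to 1/10 = 10%; the share lost is the same.

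**4. Effect on the plan's detection figure**

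Section 16.22 says six patients at the MTD give at least 82% probability of seeing a toxicity with 25% incidence: 1 − (1 − 0.25)^6 = 0.822, which reproduces. That holds only for events that reach the data. Let g be the share of affected patients whose event never rises above an uncollected grade. The documents give no value, so g is an assumption, shown over its whole range. The recorded incidence is 0.25 × (1 − g), and the detection probability is 1 − (1 − 0.25 × (1 − g))^6.

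| g | Recorded incidence | Detection in 6 patients |
|---|---|---|
| 0 | 25% | 82.2% |
| 0.25 | 18.75% | 71.2% |
| 0.5 | 12.5% | 55.1% |
| 0.75 | 6.25% | 32.1% |
| 1 | 0% | 0% |

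This applies to unlisted terms only.

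**The case against.** A short solicited list with a threshold for everything else is a legitimate design choice. On that view, all adverse events in Section 16.241 simply means all events collected, whatever their attribution. Section 18.1 leaves data submission instructions to the case report form packet, which is not among the documents and may ask for more. No decision depends on the low-grade tables: apart from the note on permanent discontinuation, the dose-limiting criteria in Section 7.16 start at Grade 3 or 4; the Phase II stopping rules in Section 16.53 use Grade 4 or higher and death; and Section 16.24 calls the Phase I toxicity results exploratory. Phase I is closed to accrual, and its patients at the MTD count in Phase II, so new terms would create two collection rules in one analysis set.

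Most of this stands as a limit on the point. It does not remove the mismatch. Section 10.62 itself states what goes on the case report forms, and Section 16 gives no floor, so a wider rule in the packet would still leave the protocol text to be reconciled.

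Several stronger readings are tempting, and the documents do not support them:

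- *The most common injection events were Grade 1.* Section 1.44 grades none of them, and the only injection-site row in Table 2 is Grade 2, which would be captured. Injection site pain is lost only when it is Grade 1, and how often that happens is not stated.
- *DC toxicity in general is undercounted by two thirds.* That figure belongs to one term and rests on two entries, in a table that may be incomplete as extracted.
- *The results cannot be compared with LS1081.* The collection rules of that trial are not given.
- *Uncollected events will be scored as zero.* The plan states no such rule. The weakness is that absence and non-collection look alike.

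**Conclusion.** The point holds as a conflict between analysis and collection. Followed as written, Section 10.6 does not supply the tables described in Sections 16.241 and 16.325, and any-grade rates for unlisted terms, including injection-site reaction and urticaria, are biased low relative to listed terms. The size cannot be fixed from the documents. The only graded illustration is urticaria, where one of three tabulated entries would be required.

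The conclusion assumes that the case report form packet asks for no more than Section 10.62 and that the lost events are not reported by an expedited route. The consequence is confined to descriptive low-grade safety tables. Dose-limiting toxicity, Grade 3+ summaries and the stopping rules are unaffected. A correction is worthwhile because safety is the Phase I primary goal and a Phase II secondary goal, and the correction is cheap.

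**What to change.** 1. **Collection.** Add injection-site reaction/pain, urticaria and allergic reaction to the Section 10.61 list for the remaining Phase II DC visits. The Section 4.1 schedule already has an adverse event assessment on every DC day, so no visit is added. Check the case report form packet first, in case it already asks for these terms.
2. **Earlier patients.** Back-fill the three terms from existing adverse event assessments where the records allow. Flag the Phase I MTD patients, and any Phase II patients treated before the change, whose terms were collected under the threshold rule.
3. **Analysis wording.** In Sections 16.241 and 16.325, limit the scope to *adverse events collected per Section 10.6*. Tabulate solicited terms at any grade separately from other terms, and head the second table with its threshold: related Grade 2, or Grade 3+. This wording change also corrects how the closed Phase I portion is reported.

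The cost is three form rows at existing visits, a modest back-filling effort and revised table headings. The drawback is that the added terms will be collected unevenly between earlier and later patients. If the team judges that worse than the gap, step 3 alone removes the contradiction but does not recover the low-grade data.

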#### 16.242 Feasibility (Goal 2.1.21)

The feasibility of the regimen will be estimated by the number of patients who received at least one dose of intratumoral DC injection divided by the total number of patients who received leukapheresis. Patient accrual rate and study completion rates will also be evaluated using summary statistics to determine if further studies of this regimen will be feasible.

#### 16.243 Quality of Life (Goal 2.1.22)

Quality of life as measured using the FACT-Lym will be utilized. The assessment will be scored according the scoring algorithm. Changes from baseline will be calculated at each assessment time points. Mean change scores at each time point will be calculated to determine if quality of life is reduced over the course of treatment. Longitudinal techniques will be employed to describe changes over time.

### 16.3 Phase II Portion

#### 16.31 Decision Rule

Pembrolizumab monotherapy induces an ORR of 39% in patients with

ipilimumab-naïve melanoma by central independent RECIST review. The potential activity of this agent in non-Hodgkin lymphoma (NHL) has not been tested. Similar check-point inhibitor Nivolumab (BMS) has reported ORR of 28% in B-cell NHL (ASH 2014). We estimate that Pembrolizumab may have similar single agent activities in NHL. Therefore we hypothesize that an ORR of 53% with this combination immunotherapy approach will be worthy of further testing in this disease population. We will explore if there is a difference in histologies enrolled in this study. Any specific NHL type with a clinical response defined as PR or CR in 2 or more patients may be expanded into a larger cohort for formal evaluation of ORR at the discretion of the PI and the Sponsor.

For phase II, the largest ORR where the proposed treatment regimen would be considered ineffective in this population is 30%, and the smallest ORR that would warrant subsequent studies with the proposed regimen in this patient population is 53%. The following one-stage design requires 28 evaluable patients (22 - 25 from phase II and 3 - 6 from the MTD portion of phase I provided that these patients have follicular lymphoma) to test the null hypothesis that the true ORR in this patient population is at most 30.

- 16.311 Interim Analysis: No interim analysis was planned for this study due to the following reasons: i) patients will be treated and evaluated for response up to two years from enrollment. ii) the total expected accrual time for this phase is only 18 – 24 months. If we were to conduct an interim analysis, all patients in the trial would have been accrued by the time patients in the interim analysis set have reached the primary endpoint for analysis.
- 16.312 Final Decision Rule: If 12 or fewer of 28 patients achieve overall response, then the proposed treatment is considered ineffective; and if 13 or more patients achieve overall response, then the treatment is considered promising and warrants further study.
- 16.313 Over Accrual: If more than the target number of patients are accrued, the additional patients will not be used to evaluate the stopping rule or used in any decision making process. If more than the target number of patients are accrued, the additional patients will not be used to evaluate the stopping rule or used in any decision making processes; however, they will be included in final endpoint estimates and confidence intervals.
- 16.314 Power and Significance Level: the power calculation is based solely on Phase II. We plan to accrue a total of 28 evaluable patients (including follicular lymphoma patients from the MTD cohort in phase I) for Phase II of the trial. This sample size provides 81% power at a one-sided type I error of 0.05 to conclude that the ORR is higher than 30% if the true ORR is 53%. Secondary analysis will be performed in which Bayesian hierarchical models (Thall et al. 2003) will be used to estimate subtype-specific ORRs for the purposes of examining differences in response and guiding future plans for subtype-specific expansion studies.
- 16.315 Other considerations: Adverse events, quality/duration of response, and patterns of treatment failure observed in this study, as well as scientific

discoveries or changes in standard care will be taken into account in any decision to terminate the study.

## 16.32 Analysis Plan

### 16.321 Primary Outcome Analyses:

16.3211 Definition: The primary endpoint of this trial is the proportion of complete responses of combination therapy with pembrolizumab, cryoablation and intra-tumor injection of autologous DC at MTD dose schedule. A success is defined as a PR or CR as the objective status during therapy. All patients meeting the eligibility criteria who have signed a consent form and have begun treatment will be evaluable for response.

16.3212 Estimation: The proportion of successes will be estimated by the number of successes divided by the total number of evaluable patients. Confidence intervals for the true success proportion will be calculated.

### 16.322 Secondary Outcome Analyses:

These analyses will include all patients meeting the eligibility criteria who have signed a consent form and have begun treatment. Analyses will include all patients enrolled in the Phase II portion of the study and analysis of each cohort separately.

16.323 Complete response (Goal 2.2.21): The response rate will be calculated, as above, in each individual cohort as supplementary to the primary analysis.

16.324 Progression free survival, treatment free survival, and duration of response (Goal 2.2.22):

Survival time is defined as the time from registration to death due to any cause. The distribution of survival time will be estimated using the method of Kaplan-Meier (Kaplan E 1958). In addition, the overall survival rate at 2 years after registration will be reported.

Treatment free survival time is defined for all evaluable patients who have achieved a response as the time from registration to next treatment or death due to any cause. The distribution of treatment-free survival will be estimated using the method of Kaplan-Meier. In addition, the disease-free survival rate at 2 years after registration will be reported.

Duration of response is defined for all evaluable patients who have achieved a PR or CR as the date at which the patient's objective status is first noted to be a response to the earliest date progression is documented. The distribution of duration of complete response will be estimated using the method of Kaplan-Meier.

16.325 Adverse Events (Goal 2.2.23): All eligible patients that have initiated treatment will be considered evaluable for assessing adverse event rate(s). The maximum grade for each type of adverse event at each evaluation will be recorded for each patient, and frequency tables will be reviewed to determine patterns. Additionally, the relationship of the adverse event(s) to the study treatment will be taken into consideration. Longitudinal analysis techniques will be utilized to determine the effect

of time on treatment adverse events.

16.326 Quality of Life (Goal 2.2.24):

Quality of life as measured using the FACT-Lym will be utilized. The assessment will be scored according to the scoring algorithm. Changes from baseline will be calculated at each assessment time points. Mean change scores at each time point will be calculated to determine if quality of life is reduced over the course of treatment. Longitudinal techniques will be employed to describe changes over time.

